4.2 Scientific Rationale for Study Design

Rationale for enrolling pediatric participants

It is expected that infants who already had RSV infection or who are seropositive present a lower virus shedding and thus a lower probability of vaccine virus transmission to their close contacts (23). In VAD00014 study, potential pediatric participants will not be screened based on their RSV baseline serostatus. Therefore, in order to maximize the probability of transmission during the study, enrolling a higher proportion of children aged 6 to 12 months may help to increase the proportion of seronegative participants and thereby increase the probability of transmission to pediatric participants receiving the placebo and / or to ad-hoc close contact participants. Some efforts will be made to enroll twins, to optimize the probability of transmission, and to limit the possible impact of age difference between the RSVt vaccine and placebo recipients. Stratification by age group could also be a way to control for the age distribution among RSVt vaccine and placebo recipients (eg, to ensure that for siblings, some younger and older children will receive RSVt vaccine).

Evaluation of Vaccine Virus Transmission

Transmission of the vaccine virus will be defined as presence of detected vaccine virus in the pediatric participants placebo-recipients and ad-hoc close contact participants, by RSVt qRT-PCR assay. Planned nasal swabs will be collected on all pediatric participants (ie, vaccinees and placebo recipients) on D01, D04, D08, D11, D15, D18, D22, D64, and D71. Nasal swabs will not be collected on D57 or D85 since vaccine virus shedding is not expected to last so long after the first administration and is expected to be lower after the second administration.

Based on an NIH study conducted with the same vaccine construct and on the same target population (20), it is expected that the probability of transmission from vaccinees to other persons will be higher when the virus shedding in the vaccinees is the highest (between 4 and 9 days after vaccine administration), so that nasal swabs will be collected regularly after the first administration to be able to detect vaccine virus. Vaccine virus shedding is expected to be lower after the second administration (8), justifying the collection of fewer nasal swabs after the second administration, and performing the interim analysis of the primary objective of transmission after the first dose.

[REDACTED]

Illness Visit(s)

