5.1 Inclusion Criteria

5.1.1 Inclusion Criteria

Participants are eligible for the study only if all of the following criteria are met:

AGE

I01. Aged 6 months to < 24 months on the day of inclusion¹

TYPE OF PARTICIPANT AND DISEASE CHARACTERISTICS

I02. Participants who are healthy as determined by medical evaluation including medical history.

I03. Born at full term of pregnancy (≥ 37 weeks) or born after a gestation period of 27 through 36 weeks and medically stable as assessed by the investigator, based on the following definition: “Medically stable” refers to the condition of premature infants who do not require significant medical support or ongoing management for debilitating disease and who have demonstrated a clinical course of sustained recovery by the time they receive the first dose of study intervention

I04. Attends a daycare facility at least 3 days per week and 4 hours per day at which the participant would be in a contact group/playroom of at least one other child 6 to < 24 months of age who will participate in this study or is a member of a household, which includes at least one other child 6 to < 24 months of age who will participate in this study

INFORMED CONSENT

I05. Informed consent form has been signed and dated by the parent(s) or other legally acceptable representative (and by an independent witness if required by local regulations)

OTHER INCLUSIONS

I06. Participant and parent/legally acceptable representative are able to attend all scheduled visits and to comply with all study procedures

¹ “6 months to < 24 months” means from the day of the 6 months after birth to the day before the 2nd birthday

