**Table 1.1: Design**

Type of design	Parallel, multi-center
Phase	II
Control method	Placebo-controlled
Study population	

Pediatric participants: Healthy infants / toddlers 6 to < 24 months of age in close contact with other infants / toddlers 6 to < 24 months of age who will participate in the study

Ad-hoc close contact participants: Ad-hoc close contact children and adults who experience acute respiratory illness (ARI) in the 28 days following the administration of the study intervention to the close contact pediatric participant

Level and method of blinding	Observer-blind: 

Blinding for study intervention group assignment: participants, parents or legally acceptable representative (LAR), outcome assessors, investigators, laboratory personnel, Sponsor study staff

No blinding for study staff who prepare and administer the study interventions

Study intervention assignment method	Pediatric participants will be screened for eligibility criteria at the time of inclusion and randomized to receive either RSVt vaccine or placebo in a 1:1 ratio. Randomization will be stratified by contact group (the household /group attended in daycare center) and by age group (< 12 months / ≥ 12 months)

Number of participants	100 pediatric participants 6 to < 24 months of age
Intervention groups	Eligible pediatric participants will be randomized in a 1:1 ratio to receive 2 intranasal administrations (56 days apart) of either the RSVt vaccine or placebo at D01 and D57
Total duration of study participation	Approximately 8 months for each pediatric participant. The duration of the ad-hoc close contacts will be limited to the Illness Visit.
Countries	United States and Puerto Rico
Use of an Independent Data Monitoring Committee, Dose Escalation Committee, or similar review group	NO

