### 3.2 Sample Size Determination

No sample size calculation was done as there are no statistical hypotheses in this study. A total of 100 pediatric participants (ie, 50 per study intervention group) are planned to be enrolled, based on clinical feasibility.

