#### 3.4.5 Other Analyses

In addition to the analysis above, subgroup analyses for vaccine virus transmission, shedding and stability would be performed by age group (<12 months,  $\geq$  12 months).

As exploratory analysis, probability of transmission of vaccine virus would be calculated for the pediatric participants using Greenwood / Reed-Frost models after each administration of study intervention. Further details are provided in [Appendix 2](#).

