## 6.2 Appendix 2 Use the Reed-Frost models and Greenwood models to estimate the transmission probability.

The binomial model is often used to estimate the transmission probability based on the idea that exposure to infection occurs in discrete contacts. Generally,  $p$  is defined as the transmission probability during a contact between a susceptible person and an infectious person. The quantity  $q = 1 - p$  is the probability that the susceptible person will not be infected during the contact, called the escape probability. In this section, the susceptible person is considered the pediatric participant who received placebo, and an infectious person is considered the pediatric participant who received RSVt vaccine.

Chain binomial models are dynamic models developed from the simple binomial model by assuming that infection spreads from individual to individual in populations in discrete units of time, producing chains of infection governed by the binomial probability distribution. The Reed-Frost and Greenwood models are examples of chain binomial models. To use these models, the number of susceptible persons and the number of infectious persons involved in each transmission generation should be known. However, in this study, the actual transmission chains is not observed, thus a single transmission generation is considered.

A contact group is defined as a group of pediatric participants who live in the same household or who attend in the same daycare center. A contact group is considered as a transmission unit and different contact groups are assumed to be separate and independent of one another. A total of  $J$  contact groups is assumed.  $S_j$  and  $I_j$  are the number of pediatric participants who received placebo and the number of pediatric participants who received RSVt vaccine in the  $j$ th contact group, respectively.  $X_j$  is the total number of pediatric participants who received placebo and have detective vaccine virus in the  $j$ th contact group.

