### ***Greenwood models***

The Greenwood model assumes that exposure to two or more infectious people at the same time is equivalent to exposure to one. That is, the probability of becoming transmitted from exposure to one or more vaccinees is still  $p$ . Then the likelihood function for estimating  $p$  is

$$L(p) = \prod_{j=1}^J \binom{S_j}{X_j} p^{X_j} q^{(S_j - X_j)}$$

The log likelihood is,

$$\log L(p) = \sum_{j=1}^J \log\left(\frac{S_j!}{S_j! (S_j! - X_j!)}\right) + \log(p) \sum_{j=1}^J X_j + \log(q) \sum_{j=1}^J (S_j - X_j)$$

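### SAP Appendix 2 (exploratory transmission models): the contact group differs from the randomization group, all vaccinees count as infectious, Greenwood keeps unexposed groups, and the log-likelihood constant is misprinted

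*SAP*

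**What the plan says.** SAP 3.4.5 introduces the models: "As exploratory analysis, probability of transmission of vaccine virus would be calculated for the pediatric participants", after each administration, with details in Appendix 2 (SAP 6.2).

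- **Contact group j.** Appendix 2 groups pediatric "participants who live in the same household or who attend in the same daycare center". SAP Table 1.1 says: "Randomization will be stratified by contact group (the household /group attended in daycare center". Inclusion criterion I04 (Protocol 5.1.1) asks that a daycare child be in a "contact group/playroom of at least one other child" in the study. Under Protocol 6.3.1 the participant number carries a contact-group identifier.
- **Infectious persons I_j.** Appendix 2 defines p for a contact between a susceptible and an infectious person, then states that "an infectious person is considered the pediatric participant who received RSVt vaccine". No shedding condition is attached. Protocol 4.2 expects that "infants who already had RSV infection or who are seropositive present a lower virus shedding", does not screen on serostatus, and expects less shedding after the second dose.
- **Greenwood.** "The Greenwood model assumes that exposure to two or more infectious people at the same time is equivalent to exposure to one". Its likelihood has S_j and X_j (placebo children, and placebo children with detected virus) but no I_j, and runs over all J groups.
- **Constant.** Both likelihoods L(p) show the usual binomial coefficient. Both log-likelihoods replace it by `S_j!/[S_j!(S_j! − X_j!)]`.

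**The concern.** A chain-binomial estimate depends on who is counted as a source for whom. The SAP holds two definitions of the group, so two programmers could build different data sets from the same children. Under the wider definition, Reed-Frost spreads each transmission over vaccinees in other rooms. Counting vaccinees who never shed gives a quantity different from the one Appendix 2 defines. Keeping placebo children with no vaccinee in their group treats them as having escaped an exposure they did not have. Where each of these acts, the estimate falls. For a live vaccine whose transmission data are meant to inform a large Phase III study, that is the uncomfortable direction. The misprinted constant matters only to someone who codes the log-likelihood as printed.

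**Working it through.** **The plan's own example.** Appendix 2 takes S = 2 placebo children and I = 3 vaccinees. At p = 0.10, q = 0.90:
- both escape: q^6 = 0.531441
- exactly one positive: 2 × (1 − q^3) × q^3 = 2 × 0.271 × 0.729 = 0.395118
- both positive: (1 − q^3)^2 = 0.073441

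These sum to 1. The example and the printed Reed-Frost L(p) agree.

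**Inputs.** The documents give no group sizes, rooms per center or transmission rates, so the layouts and event counts below are assumptions. The 88% comes from Protocol 2.2 (NIH vaccine, seronegative children; the other NIH study, n = 20, reports 100%). Reading infectivity as the share who shed is also an assumption.

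**1. Center instead of room.** If a fraction a of placebo children are positive and every group has I vaccinees, the Reed-Frost estimate is `1 − (1 − a)^(1/I)`.

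| Assumed layout | By room | By center |
|---|---|---|
| 3 rooms of 1 + 1, a = 0.20 | 0.200 | 1 − 0.80^(1/3) = 0.072 |
| 2 rooms of 2 + 2, 6/24 positive | 1 − 0.75^(1/2) = 0.134 | 1 − 0.75^(1/4) = 0.069 |
| 3 rooms of 2 + 2, 6/36 positive | 1 − 0.8333^(1/2) = 0.087 | 1 − 0.8333^(1/6) = 0.030 |

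Greenwood as printed is ΣX_j/ΣS_j, so pooling leaves it at 0.20, 0.25 and 0.167. Once Greenwood is restricted to exposed groups, pooling matters only if a room without a vaccinee is merged with one that has a vaccinee.

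**2. All vaccinees counted.** In pairs, if a share s of vaccinees shed and true p per shedder is 0.20, both models are expected to give 0.20 × s: 0.176 at s = 0.88, and 0.100 at an assumed s = 0.50. In ten rooms of 2 + 2 with one shedder each and 4/20 placebo children positive, Reed-Frost gives 1 − 0.80^(1/2) = 0.106 counting vaccinees and 0.200 counting shedders. Greenwood gives 0.200 both ways, because every room has a shedder.

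**3. Groups with no vaccinee.** Take 40 exposed placebo children with 8 positive, plus 10 unexposed and negative. Greenwood is 8/40 = 0.20 without the unexposed children and 8/50 = 0.16 with them. Reed-Frost is 0.20 both ways, since such a group contributes q^0 = 1. If a placebo child in a group with I_j = 0 were positive, the factor (1 − q^0) would make the Reed-Frost likelihood zero for every p.

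Such groups are possible because randomization is also stratified by age. If the strata are independent contact-group-by-age cells, a pair split across age strata is both placebo with probability 0.5 × 0.5 = 0.25. For a pair in one stratum it is 0 with blocks of two and 1/6 = 0.167 with blocks of four. The block size is not stated.

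**4. Printed constant.** The correct value is `S_j!/[X_j!(S_j − X_j)!]`.

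| S, X | Printed | Correct |
|---|---|---|
| 1, 0 | 1/[1 × (1 − 1)], undefined | 1 |
| 1, 1 | 1/[1 × (1 − 1)], undefined | 1 |
| 2, 1 | 2/[2 × (2 − 1)] = 1 | 2 |
| 2, 2 | 2/[2 × (2 − 2)], undefined | 1 |
| 3, 1 | 6/[6 × (6 − 1)] = 0.2 | 3 |

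It is undefined whenever X_j = S_j, including the SAP's own case of both placebo children infected, and at S_j = 1, the placebo count in a discordant pair. The term has no p in it, so correcting or dropping it leaves the estimate and interval unchanged.

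**5. Zero events.** If all X_j = 0, the Reed-Frost likelihood is q^(ΣI_jS_j). The exact two-sided 95% upper limit is `1 − 0.025^(1/ΣI_jS_j)`, which for 50 contacts is 0.071. Appendix 2 does not say how its interval is formed.

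**The case against.** The strongest reply is that little rests on this analysis. It is exploratory, and of the sample size the SAP says "No sample size calculation was done as there are no statistical hypotheses in this study". The primary transmission result is the proportion of placebo children with detected virus, with a Clopper-Pearson interval. That stands, and it limits the severity.

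On the contact group, Protocol 4.1 itself speaks of siblings or children at the same daycare center, so Appendix 2 may only repeat a shorthand. If each center enrolls one room, nothing changes, and transmission between rooms would weaken the case for the narrower group. That also stands as a limit on size, but the SAP still gives two definitions.

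On vaccinees, Appendix 2 says openly whom it treats as infectious, and per-vaccinee transmission is a coherent quantity. Granted, but p is not labelled that way. The per-protocol set excludes children exposed to RSV before dosing, which would help in part, yet Appendix 2 names no analysis set.

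On unexposed groups, the Greenwood text defines p for exposure to one or more vaccinees, so an analyst might drop them unprompted. The formula does not say so.

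A reader might infer that the first three problems lower both models alike. They do not: pooling and non-shedders act mainly on Reed-Frost, and unexposed groups act only on Greenwood. A reader might also infer that the misprint makes the analysis impossible. L(p) is printed correctly and no code is shown, so this would happen only if the log form were coded literally. Nor do the documents support saying that the interval collapses at zero events, because no Wald interval is specified.

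**Conclusion.** The point holds as a moderate one, confined to the exploratory models.

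- The contact-group definitions conflict. Reed-Frost is biased down if a center has several enrolled rooms and transmission is within rooms. The fall from 0.20 to 0.072 belongs to one assumed layout.
- The estimate is per vaccinee, not per infectious contact. At the cited 88% the gap in pairs is 0.20 against 0.176. Larger gaps need shedding rates that the documents do not give. Greenwood is affected only where no vaccinee in the group sheds.
- Unexposed groups lower Greenwood only. How many will occur cannot be derived from the documents.
- The constant is wrong in both log-likelihoods and changes no estimate. Its appearance in both formulas argues against a text-extraction fault, but the source PDF should be checked.

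It would be wrong to conclude that the primary transmission result is compromised, since it does not use Appendix 2.

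**What to change.** In SAP Appendix 2:

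1. Define j as the contact group recorded in the IRT: household, or daycare group/playroom.
2. Restrict both likelihoods to groups with I_j ≥ 1 vaccinee, and list any placebo positives in groups without one.
3. Label the all-vaccinee estimate as per-vaccinee transmission. Add a sensitivity estimate with I_j equal to the number of vaccinees with at least one swab ≥ LOD in the relevant post-dose period. List placebo positives in groups with no detected shedder, so that they are not silently dropped. This matters most after dose 2, when only D64 and D71 are swabbed.
4. Replace the constant by `S_j!/[X_j!(S_j − X_j)!]`, or omit it.
5. If all X_j = 0, report an exact upper limit: `1 − 0.025^(1/ΣI_jS_j)` for Reed-Frost and the Clopper-Pearson limit for Greenwood.

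The cost is SAP wording and a few lines of code, and all inputs are already collected. The drawback is that groups without a detected shedder leave the sensitivity estimate, which is why the listings are needed.

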### ***Reed-Frost models***

The Reed-Frost model assumes that exposure to two or more infectious people at the same time are independent exposures.

Suppose a contact group with five pediatrics, where two received placebo and three received RSVt vaccine. The probability that a pediatrics who received placebo escape transmission from all the three pediatrics who received RSVt vaccine is calculated as  $q^3$ , so the probability of getting transmitted is  $1 - q^3$ . The probability that all two placebo-pediatrics escape transmission from all three pediatrics who received RSVt vaccine is  $q^{3*2}$ . Similarly, the probability that all the two placebo-pediatrics get transmitted is  $(1 - q^3)^2$ .

Then based on the Reed-Frost model, the likelihood function for estimating  $p$  is

$$L(p) = \prod_{j=1}^J \binom{S_j}{X_j} (1 - q^{I_j})^{X_j} q^{I_j(S_j - X_j)}$$

The log likelihood is,

$$\log L(p) = \sum_{j=1}^J \log\left(\frac{S_j!}{S_j! (S_j! - X_j!)}\right) + \sum_{j=1}^J X_j \log(1 - q^{I_j}) + \log(q) \sum_{j=1}^J (S_j - X_j) I_j$$

### ***Greenwood models***

The Greenwood model assumes that exposure to two or more infectious people at the same time is equivalent to exposure to one. That is, the probability of becoming transmitted from exposure to one or more vaccinees is still  $p$ . Then the likelihood function for estimating  $p$  is

$$L(p) = \prod_{j=1}^J \binom{S_j}{X_j} p^{X_j} q^{(S_j - X_j)}$$

The log likelihood is,

$$\log L(p) = \sum_{j=1}^J \log\left(\frac{S_j!}{S_j! (S_j! - X_j!)}\right) + \log(p) \sum_{j=1}^J X_j + \log(q) \sum_{j=1}^J (S_j - X_j)$$

### ***Maximum Likelihood Estimation***

The maximum likelihood is used for parameter estimation. The basic idea behind maximum likelihood estimation is to find the value  $\hat{p}$  which is most likely to have produced the data. The statistic  $\hat{p}$ , if it exists, is called the maximum likelihood estimate of  $p$ . Maximizing  $L(p)$ , the probability of observing the actual data, is equivalent to minimizing the negative log likelihood,  $-\log(L)$ .

SAS/IML procedure is used to compute maximum likelihood estimate and the 95% confidence interval for  $p$ .

